The hardware and software are not FDA cleared, but also not FDA regulated as they are not medical devices. According to the FDA, a medical device is intended to diagnosis and or treat diseases while affecting the structure or function of any part of the body (<https://www.fda.gov/MedicalDevices/DeviceRegulationandGuidance/Overview/ClassifyYourDevice/ucm051512.htm>). This is not the case for our study as our participants will already be diagnosed with PFP by a medical professional (we will not change this diagnosis) and our protocol will not alter any function or structure of the human body. Our leg press task is simply used to facilitate naturally occurring movement of the leg and hip and not intended to treat patellofemoral pain. Our method is simply to further our understanding of the neural mechanisms underlying natural movement in this population.

(5) DURATION:

Each participant will participate in 1 planned study visit that may take up to 3 hours. Data analysis will continue for a 2 year period following the final enrollment.

(6) SELECTION & RECRUITMENT OF PARTICIPANTS

We aim to recruit approximately 30 healthy female volunteers with PFP. Only females will be recruited for this study as they are 2 to 10 times more likely to develop PFP than males³⁰⁻³². Females participants with PFP (age 7-40 years old) will be recruited from local school districts, local sports clubs and teams, local colleges, adult sport leagues, and professional sports teams, through our well established network with area coaches and athletic trainers. Questions regarding participation will be answered during the presentations or through e-mail or phone. Participants will be contacted via telephone to further explain the study, answer any additional questions and to enroll them in the study. The participants and parents/guardians (if subject under age of 18) who voluntarily agree to participate will be scheduled to complete the pre-participation testing. The participant and parent/guardian (if subject under the age of 18) will read and sign the “Consent to Participate in a Research Study” form, approved by the Institutional Review Board of Cincinnati Children’s Hospital. If the participant and parent/guardian does not read or sign the form, they will not participate in the study. Adult volunteers will be recruited via word of mouth or through affiliations with the teams/clubs noted above.

Inclusion criteria

- Normal female healthy volunteer aged 7-40

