DTI data will first be subjected to preprocessing to correct for Eddy current and head motion artifact, followed by calculation of the three diffusion eigenvectors and eigenvalues. DTI measures, including fractional anisotropy (FA), mean diffusivity (MD), axial diffusivity (AD), and radial diffusivity (RD) will be calculated. The regions of interest will be manually determined in major white matter areas such as corpus callosum, internal capsule, and external capsule. After being normalized to a common template, voxel based group analysis can be performed to explore brain regions that present significant group difference or longitudinal changes. Fiber tracking can be performed to generate white matter tracts in different areas in the brain, e.g., cortico-spinal tract, different segments in corpus callosum, optic radiation, cingulum superior longitudinal fasciculus, and others.

Functional fMRI (resting state fMRI) will also be subjected to routine image pre-processing pipeline. Functional connectivity analysis will be performed, using the CONN toolbox, <http://www.nitrc.org/projects/conn/>) between all brain regions that are involved in the proper functioning of default mode network, sensory motor network, visual network, and a series of other networks that are known to be strongly functionally connected during resting state.

(10) FACILITIES AND PERFORMANCE SITES:

All MRI scanning will be performed in the Imaging Research Center (IRC) in the Cincinnati Children's Hospital Research Foundation (CCHRf). Sedation will not be used for any of the test visits. The entire MRI series, including anatomical imaging, DTI, and fMRI, will be completed in 75 minutes or less.

(11) POTENTIAL BENEFITS:

Participants of this study will not receive any direct or immediate benefits by completing this study. However, they will be contributing to research involving the potential for major contributions to future PFP intervention and prevention strategies.

(12) POTENTIAL RISKS, DISCOMFORTS, INCONVENIENCES AND PRECAUTIONS:

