Data Storage. There is also a minimal risk that the data collected for each participant may be viewed by individuals outside the research team. The risk that confidential data may be viewed is relevant for both the written forms and electronic databases. Precautions, such as password-

protected computers, locked cabinets and coded identification numbers, are in place to minimize this risk.

Adverse Events. As described in the consent, if a participant believes they have sustained an injury as a result of the study then they are instructed to contact the principal investigator or director of social services who in turn will then contact CCHMC IRB and necessary funding institutions, as aforementioned. If a participant sustains an injury during testing they will be referred to the most appropriate medical facility or seek medical attention by the physician/medical specialist of their choice.

(13) RISK/BENEFIT ANALYSIS:

Participants will be approached for participation via the appropriate method. The purpose and the study protocol will be fully explained in conversation and with the informed consent process.

On the day of the study, the investigators will confirm that the volunteer participant has no health impairment as outlined in the exclusion criteria. Time will be taken to repeat the aims of the study, test protocol, and to answer any remaining questions posed by the participant.

The methods described in this protocol have been used extensively in previous testing with our research team. During previous MRI/fMRI testing, there have been no reported injuries, adverse events or complications. Additionally, the investigators have considered potential risk for injury and have taken additional steps, described in the protocol, to minimize these risks.

(14) DATA SAFETY & MONITORING:

[name] will serve as a study monitor for this project for any incidental findings, while the PI and study coordinators will be responsible for monitoring data quality and adverse events. The monitor will review adverse events and unanticipated events at the time they occur and will report his assessment of the event(s) to the PI.

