This research study involves only minimal risk for participants (see Risk/Benefit Analysis section (15)). Further assurances regarding participant safety and protection of private and confidential participant information have been outlined in the Potential Risks, Discomforts, Inconveniences and Precautions section (14), the Privacy section (18) and the Confidentiality section (19). If during the, preliminary analyses the research team identifies strong evidence of harm from the Q-collar device the study will be stopped immediately.

(15) PRIVACY AND CONFIDENTIALITY:

The participant has the right to privacy. The investigators will protect participant privacy to the extent allowed by law. All facts about this study that can describe a participant's name will be kept private. Results of the study will be summarized regarding age, etc. but the investigators will take every precaution necessary to keep names private.

To maintain the privacy information of study participants, only pertinent research personnel will have access to participant information. Research personnel are employees of CCHMC and have been trained in human participant's research and HIPAA compliance. To further insure privacy, all data will be analyzed and tracked using a coded identification number that does not use

identifiable personal information. Personal information and identifiers will be securely recorded and filed by the administrative assistant. The data will be encrypted with a password and stored on a personal computer and backed up on a network drive. The participant identification code will be used on all data questionnaires.

The results of this study will be kept confidential. No participant identification will be made public record in any form unless the participant gives his or her expressed written permission of release of participant's name, photograph or likeness captured on video. The investigators will be available for any questions that may arise.

To further insure confidentiality, only pertinent research personnel will have access to participant information. Research personnel are employees of CCHMC and have been trained in human subjects research and HIPAA compliance.

(16) COST OF PARTICIPATION:

Participants will endure no costs other than time and effort in participating in this study. Insurance will not be billed for any of the tests associated with this study.

(17) PAYMENT FOR PARTICIPATION:

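### The only study-level stopping statement (Protocol Section 14) is tied to a Q-collar device that this study does not use, and all four section references in the same paragraph are wrong

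*Protocol*

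**What the plan says.** The second paragraph of Section 14 does three things.

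- It describes the study as minimal risk and refers the reader to another section: "This research study involves only minimal risk for participants (see Risk/Benefit Analysis section (15".
- It refers to further safeguards by title and number: "Precautions section (14), the Privacy section (18) and the Confidentiality section (19".
- It closes with a conditional stopping statement: "preliminary analyses the research team identifies strong evidence of harm from the Q-collar device the study will be stopped immediately".

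The first paragraph of Section 14 makes the principal investigator and coordinators responsible for monitoring data quality and adverse events. It also has a study monitor review adverse and unanticipated events when they happen and report the assessment to the principal investigator.

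On equipment, Section 4 states: "The hardware and software are not FDA cleared, but also not FDA regulated as they are not medical devices". The apparatus it goes on to mention is the leg press: "Our leg press task is simply used to facilitate naturally occurring movement of the leg and hip".

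**The concern.** A stopping statement should cover the exposures that participants actually receive. This one names a product that the study does not use, so its condition cannot arise. The procedures that could cause harm fall outside it. They include movement of a painful knee and direct pressure on the patella, in participants who may be as young as 7 (Section 6).

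An IRB member or monitor who turns to Section 14 for study-level protection finds a rule about something else. If they follow the section numbers given there, they reach the wrong section or none. The matter at stake is the clarity of the safety provisions; the statistical results are not touched.

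**Working it through.** No arithmetic applies beyond counting. The check compares the paragraph with the rest of the protocol.

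**1. Is there a Q-collar in the study?** The term occurs once in the protocol, in the stopping sentence. The sections where a study device would be described show the following:

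- Section 4 (Study Design): T1-weighted imaging, diffusion tensor imaging, resting-state and task fMRI, lower-extremity movement tasks, and 15 minutes of intermittent manual pressure. There is no collar. The study's hardware and software are said not to be medical devices.
- Section 6 (Selection & Recruitment): no criterion concerns wearing a collar.
- Section 8 (Study Procedures): questionnaires, MRI, the knee and hip task, the quadriceps contraction task, manual pressure, and a VAS pain rating after each fMRI task. There is no collar.
- Section 9 (Data Analysis/Methods): no collar exposure or comparison.
- Section 12 (Potential Risks): MRI risks, data storage and injury referral. No collar risk is listed.

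**2. Is there another study-level stopping statement?** No. The remaining safety provisions work event by event (Section 14, first paragraph; Section 12, Adverse Events) or participant by participant (removal from the scanner on request, Sections 8 and 12).

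**3. Do the paragraph's section references match the headings?**

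| Topic | Number cited in Section 14 | Actual heading | Result |
|---|---|---|---|
| Risk/benefit | 15 | "13) RISK/BENEFIT ANALYSIS" | wrong section |
| Potential risks | 14 | "12) POTENTIAL RISKS, DISCOMFORTS, INCONVENIENCES AND PRECAUTIONS" | wrong section |
| Privacy | 18 | "15) PRIVACY AND CONFIDENTIALITY" | no such section |
| Confidentiality | 19 | the same combined Section 15 | no such section |

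The last numbered section is (17), so 18 and 19 do not exist. All 4 of the 4 references are wrong, and 2 of the 4 lead nowhere.

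**4. What explains it?** The words are legible and complete, so neither redaction nor PDF extraction accounts for them. A foreign device name, together with numbering that fits a different set of sections, suggests text taken from another protocol. The device name is the stronger evidence, because wrong numbers alone could come from merging or renumbering sections of this document. The finding does not depend on where the text came from.

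**The case against.** The strongest case on the other side concerns weight. No one disputes the text.

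- The sentence gives one sufficient condition for stopping and does not say that the study stops only then. It takes away no authority to halt for other reasons. This stands.
- Harm from the real procedures is handled elsewhere. Besides the monitor's review, Section 12 provides that a participant who believes they were injured contacts the principal investigator or the director of social services, who then contacts the IRB and the funding institutions. Medical referral is also provided for. None of this relies on the faulty sentence. This stands.
- Each wrong reference also gives the section's title, and the titles lead a careful reader to the right place. This stands, and it makes the numbering errors clerical. They would not merit a comment on their own.
- Deleting the stopping sentence would also remove the contradiction, and a single-visit, minimal-risk study may not need such a statement. It is true that deletion would cure the inconsistency. However, the protocol chose to make a study-level safety commitment, and restating it correctly costs no more than removing it and keeps that commitment.

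These points limit the seriousness. They do not make the sentence correct, since a stated safety rule still refers to something outside the study.

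**Conclusion.** The concern holds. The protocol's only study-level stopping statement names a device used nowhere in the study, so it cannot be triggered by the MRI, the motor tasks or the manual knee pressure. All four cross-references in the same paragraph carry the wrong number. Confidence is high, because the conclusion rests on the full text of the protocol and needs no outside assumption. Only the carry-over explanation is an inference.

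This should be fixed, but its practical impact is small. There is one visit of up to 3 hours, the study is described as minimal risk, events are reviewed as they occur, participants can have themselves removed from the scanner at once, and the principal investigator remains free to halt the study.

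**What to change.** In Section 14, replace the reference to the Q-collar with this study's own procedures: MRI, the lower-extremity motor tasks, and manual pressure on the quadriceps and patella. Base the stopping decision on the adverse event review that the section already describes. For example: *If review of adverse or unanticipated events gives strong evidence of harm from the MRI, the motor tasks or the manual knee pressure, the study will be stopped immediately.* The investigator and IRB may decide whether the VAS ratings already collected after each fMRI task should also inform that decision.

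In the same paragraph, correct the references to Risk/Benefit Analysis (13), Potential Risks (12), Privacy (15) and Confidentiality (15).

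The cost is a one-paragraph protocol amendment, with no new data collection and no change to the sample size or analysis.
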